1. INTRODUCTION

The purpose of this Statistical Analysis Plan (SAP) is to describe the analyses to be included in the Clinical Study Report for Protocol HBPCOVID02.

2. SUMMARY OF KEY PROTOCOL INFORMATION

2.1. Study Objective(s) and Endpoint(s)

Objectives	Endpoints	
Primary Objective	Primary Endpoint	
 To investigate the efficacy of intravenous infusions of HB-adMSCs (allogeneic) vs. Placebo in patients with Chronic Post-COVID-19 Syndrome as determined by improvements in individual symptom scores of Visual Analog Scale of Neurological Symptoms. (Time frame: Baseline to Week 26). To assess the safety of intravenous infusions of HB-adMSCs (allogeneic) vs. Placebo in patients with Chronic Post-COVID-19 Syndrome as determined by the incidence of adverse events or serious adverse events (Time frame: Baseline to Week 26). 	 The efficacy and safety primary endpoints of this study will be evaluated by assessing changes from Baseline to Weeks 26 in the following: Changes in the Visual Analog Scale of Neurological Symptoms. VAS are psychometric measuring tools intended to document the characteristics of disease-related symptom severity in individuals. The neurological symptoms included in this scale are (1) extreme fatigue (2) 3 brain fog, (3) headache (4) sleep disturbances (5) loss of taste/smell. Incidence of treatment-emergent Adverse Events (TEAEs) and serious Adverse Events (SAEs). Incidence of AEs of special interest (serious or nonserious), including thromboembolic events, infections, and hypersensitivities Changes in laboratory values, vital signs, weight, physical exam results, and medications used to treat Chronic Post-COVID-19 Syndrome. 	
Secondary Objective	Secondary Endpoint	
• To investigate the efficacy of intravenous infusions of HB-adMSCs (allogeneic) vs. Placebo in patients with Chronic Post-COVID-Syndrome as determined by	The efficacy and safety secondary endpoints of this study will be evaluated by assessing changes from Baseline to Weeks 26 in the following:	

Objectives	Endpoints
 improvements in individual symptom scores of Visual Analog Scale of Non-Neurological Symptoms. (Time frame: Baseline to Week 26). To evaluate the efficacy of intravenous infusions of HB-adMSCs (allogeneic) vs. Placebo in patients with Chronic Post-COVID-Syndrome as determined by changes in Fatigue Scale (Time frame: Baseline to Week 26). To assess the efficacy of intravenous infusions of HB-adMSCs (allogeneic) vs. Placebo in patients with Chronic Post-COVID-19 Syndrome as determined by changes in SF-36 Quality of life self-assessment. (Time frame: Baseline to Week 26). To identify the safety of intravenous infusions of HB-adMSCs vs. Placebo in patients with Chronic Post-COVID-19 Syndrome as determined by changes in SF-36 Quality of life self-assessment. (Time frame: Baseline to Week 26). To identify the safety of intravenous infusions of HB-adMSCs vs. Placebo in patients with Chronic Post-COVID-19 Syndrome as determined by changes in fusions of HB-adMSCs vs. Placebo in patients with Chronic Post-COVID-19 Syndrome as determined by changes in fusions of HB-adMSCs vs. Placebo in patients with Chronic Post-COVID-19 Syndrome as determined by changes in Patient Health Questionnaire (PHQ-9). 	 Changes in Subject's energy and stamina as evidenced on the Fatigue Assessment form. Changes in Visual Analog Scale of non -Neurological Symptoms. The symptoms included in this scale are (1) dyspnea a rest and with activity, (2) cough, (3) body aches, and (4) joint pain. Changes in Subject's quality of life as evidenced by the Short Form 36 Health Survey Questionnaire. Changes in Subject's level of depression as evidenced by the PHQ 9 scale.

2.2. Study Design

Overview of Study Design and Key Features				
	Placebo: 20ml sterile saline			
	 Dose: N/A 			
	 Route: Intravenous 			
	 Regimen: Weeks 0, 2, 6, and 10. 			
	• Duration of administration: 1 hour			
	• Study treatment details,			
	Placebo HB-adMSCs (allogencic)			
	Manufacturer Baxter or an equivalent manufacturer Hope Biosciences			
	Dosage 20 ml sterile saline $2 \times 10^{-8} \pm 20\%$ cells			
	suspended in 20 ml sterile saline			
	Route Intravenous Intravenous			
	Administration Rate 4-5 ml/min 4-5 ml/min			
	Syringe will contain 20 ml of Syringe will contain 20 ml of			
	Preparation sterile saline. allogeneic HB-adMSCs. Placebo should be diluted in 250 ml of 0.9% Sodium chloride. HB-adMSCs should be diluted in 250 ml of 0.9% Sodium chloride.			
Study	• Participants will be randomised 1:1 to receive HB-adMSCs active			
Intervention	treatment or Placebo.			
Assignment				
Interim	No interim analysis planned			
Analysis				

3. STATISTICAL HYPOTHESES

The primary analysis will test whether HB-adMSCs is superior to Placebo according to the following statistical hypotheses:

Null hypothesis H0: The difference in change from baseline to Weeks 26 in Visual Analog Scale of Neurological Symptoms score between treatment groups (HB-adMSCs – Placebo) is equal to zero.

Alternative hypothesis H1: The difference in change from baseline to Weeks 26 in Visual Analog Scale of Neurological Symptoms score between treatment groups (HB-adMSCs – Placebo) is not equal to zero.

Secondary analysis will be tested for mean difference for change from Baseline to Week 26 for efficacy endpoints for both treatment groups,

Null hypothesis H0: $\Delta = 0$ Alternative hypothesis H1: $\Delta \neq 0$

3.1. Multiplicity Adjustment

The Bonferroni-Holm method for adjustment of multiplicity adjustment is performed for all secondary efficacy endpoint of interest.

Bonferroni-Holm method starts with ordering the p-values in increasing order and starts with testing the hypothesis with the lowest p-value on the 2.5/k% level (one-sided), where k is the number of hypotheses in the procedure. If significant, the testing proceeds to comparing the next lowest p-value with 2.5/(k-1) %.

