5.1.1. General Methodology

Unless otherwise stated, all hypotheses will be tested at a 2-sided significance level of 0.05 and 95% confidence interval. All continuous measurements will be summarised descriptively at each visit by treatment using observed data.

Summary of continuous variables will be presented using N, Mean, 95% confidence interval of mean, Standard Error of mean (SE), Standard Deviation (SD), Median and Range (Minimum and Maximum). The categorical variables will be presented using number and percentage based on N.

For measurements over time mean values will be plotted to explore the trajectory over time. Observed data will be used as the basis for plotting data along with bars as +/- SE, not otherwise specified.

As a primary analysis, a standard Analysis of Covariance (ANCOVA) will be applied for primary and secondary endpoint to test the significance of the effects of the treatment at Week 26. The model includes treatment as fixed factor and the corresponding baseline value as a covariate.

A parametric Repeated Measures Analysis (RMA) Model will be applied as a secondary analysis to test the significance of the effects of the treatment at Week 2, Week 6, Week 10, Week 14, Week 20 and Week 26 including baseline as covariate.

Presentation of results from a statistical analysis model will include the estimated mean treatment effects (Least Square Means (LSMeans)). For all endpoints analysed statistically, estimated mean treatment differences will be presented together with two-sided 95% confidence intervals and p-values,

HB-adMSCs - Placebo

Pairwise t-test will be performed on the efficacy endpoints to test the difference between baseline and week 26 (EOS) as secondary analysis. Data for all the efficacy outcomes will be checked for normality (Shapiro-Wilk Test).

When there is a larger deviation of data distribution from normality, appropriate nonparametric test will be used.

Study population analyses including analyses of subject disposition, demographic and baseline characteristics, medical history, prior and concomitant medications.

Disposition summary includes, subject screened, randomized and disposition at end of study – Week 26 along with reasons for withdrawals. Subjects in different analysis populations also will be presented.

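### SAP 3.1 sets one-sided Holm thresholds while the rest of the SAP is two-sided; entering the planned two-sided p-values would test the secondary family at 2.5% instead of 5%

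*SAP*

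**What the plan says.** SAP 3.1 states that the Holm adjustment "is performed for all secondary efficacy endpoint of interest". The ordered p-values are handled by "testing the hypothesis with the lowest p-value on the 2.5/k% level (one-sided"), "where k is the number of hypotheses in the procedure". The next step is: "If significant, the testing proceeds to comparing the next lowest p-value with 2.5/(k-1") %. The side is named at the first step only, and k is given no value.

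SAP 3 states the secondary null hypothesis as a zero mean difference and the alternative as a non-zero one, with no direction.

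SAP 5.1.1 sets the general rule: "Unless otherwise stated, all hypotheses will be tested at a 2-sided significance level of 0.05 and 95% confidence interval". It fixes the contrast as HB-adMSCs minus Placebo and reports estimated differences with two-sided 95% intervals and p-values. SAP 5.2.2 repeats that format, and SAP 5.3.1 applies the 5.2.2 models to the secondary endpoints.

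The protocol's Statistical Methods section says only that post-hoc comparisons will be corrected for multiplicity. It gives no method, level or side.

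**The concern.** A Holm rule has two parts that must match: the kind of p-value that is ordered, and the thresholds it is compared with. Here the thresholds belong to one-sided p-values, while the hypotheses, the default level and the intervals point to two-sided ones. Nothing in the SAP converts one to the other.

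Two analysts could therefore follow the same text and disagree. One takes the model's two-sided p-values and compares them with 2.5/k%. The other forms one-sided p-values and has to choose a direction for each endpoint. A secondary endpoint whose two-sided p-value lies between the two candidate thresholds would be declared significant by one and not by the other. The wording about endpoints of interest adds a second open choice, because it leaves k to be settled later.

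**Working it through.** **Inputs**
- Thresholds 2.5/k%, then 2.5/(k-1)%, labelled one-sided: SAP 3.1.
- Two-sided secondary alternative: SAP 3.
- Two-sided 0.05 by default: SAP 5.1.1.
- 1:1 allocation (SAP 2.2) and 80 subjects (SAP 6), hence 40 per arm if nobody is lost.
- k: not stated. I take k = 4, the four bullets in SAP 5.3.1 (FAS, non-neurological VAS, SF-36, PHQ-9).
- Standardised effect d: not stated in either document. I use 0.5, 0.63 and 0.8 as assumptions.

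**Step 1: the thresholds as labelled.** A one-sided test at 0.025/k has critical value z(1 - 0.025/k). A two-sided test at 0.05/k has critical value z(1 - (0.05/k)/2), which is the same number. For k = 4 both are 2.498. With one-sided p-values, the rule in SAP 3.1 is therefore a correct Holm procedure and loses no power for an effect in the chosen direction.

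**Step 2: the same thresholds with two-sided p-values.** The familywise bound is k × (0.025/k) = 0.025, half of 0.05, for every k. For k = 4 the first critical value rises from 2.498 to 2.734. With four independent endpoints the actual familywise rate at the first step is 1 - (1 - 0.00625)^4 = 0.0248, against 1 - (1 - 0.0125)^4 = 0.0491 with 5/k%.

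**Step 3: thresholds for two-sided p-values, k = 4**

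| Step | 2.5% divided by hypotheses left | 5% divided by hypotheses left |
|---|---|---|
| 1 | 0.00625 | 0.0125 |
| 2 | 0.00833 | 0.0167 |
| 3 | 0.0125 | 0.025 |
| 4 | 0.025 | 0.05 |

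A smallest two-sided p-value between 0.00625 and 0.0125 passes or fails according to the reading.

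**Step 4: illustrative power at the first step.** Two-sample t-test, n = 40 per arm, 78 degrees of freedom, noncentrality d × √(n/2) = d × √20.

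| d (assumed) | Noncentrality | Two-sided p against 0.0125 | Two-sided p against 0.00625 | One-sided p against 0.00625 |
|---|---|---|---|---|
| 0.5 | 2.236 | 0.380 | 0.291 | 0.380 |
| 0.63 | 2.817 | 0.604 | 0.506 | 0.604 |
| 0.8 | 3.578 | 0.843 | 0.776 | 0.843 |

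The loss is about 7 to 10 percentage points, and it appears only in the fourth column.

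**Step 5: how open k is.** If PHQ-9 is left out, because the secondary objectives treat it as safety while SAP 5.3.1 lists it under efficacy, k = 3. If symptoms and SF-36 dimensions are counted separately, k = 1 (FAS) + 4 (VAS symptoms) + 8 (SF-36 dimensions, per the protocol) + 1 (PHQ-9) = 14, or 15 if dyspnea at rest and with activity are scored apart. The first two-sided threshold at 5/k% runs from 0.0167 (k = 3) to 0.0033 (k = 15).

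**The case against.** The strongest reply is that 2.5% one-sided is the ordinary counterpart of 5% two-sided, so SAP 3.1 taken literally costs nothing. Step 1 confirms this. A reader might infer that following the SAP as written halves the secondary alpha. The documents do not support that, because the halving requires the analyst to disregard the one-sided label.

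A second reply is that the default in 5.1.1 opens with an exception clause, so 3.1 may be a deliberate exception. That is a fair reading of 5.1.1, and it means that not every test in the SAP can be called two-sided. The side of the reported p-values is implied by the hypotheses, level and intervals, not written out. But the exception would still contradict the two-sided secondary alternative in SAP 3, the parent section of 3.1.

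A third reply is that the directions are obvious. This holds in part. The contrast is fixed in 5.1.1, the protocol describes VAS as running from no symptoms at zero to worst at ten, and it scores PHQ-9 items from 0 to 3 by frequency. The documents give no scoring direction for FAS or SF-36, and no direction of benefit is tied to the test of any secondary endpoint.

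Finally, the halving reading is conservative: it cannot inflate type I error, it leaves the primary endpoint alone, and it affects secondary tests in a phase 2 trial. All of that stands and limits the weight of the point. It does not remove the ambiguity.

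**Conclusion.** The inconsistency is real: SAP 3.1 is one-sided, SAP 3 and the default in 5.1.1 are two-sided, and no text says which p-value enters the Holm rule. The thresholds themselves are not wrong. If the planned two-sided p-values are entered, the secondary family is tested at 2.5% instead of 5%; this is exact and depends on neither k nor effect size.

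The power figures are illustrations. They assume k = 4, 40 per arm, a two-sample t-test and the stated values of d. SAP 5.3.1 makes the repeated-measures model primary for these endpoints, and the efficacy set is limited to participants who received all four infusions, so actual power would differ. The point merits a clarification before unblinding; it does not threaten the primary conclusion.

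**What to change.** In SAP 3.1, delete the one-sided label and state that the two-sided p-values from the treatment comparison are ordered and compared with 5/k%, 5/(k-1)% and so on. This agrees with SAP 3 and 5.1.1. Replace "all secondary efficacy endpoint of interest" with the named list of hypotheses, so that k is a number fixed before unblinding. That list should settle whether PHQ-9 belongs to the efficacy family and at what level the VAS symptoms and SF-36 dimensions are counted.

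Keeping 2.5/k% would also be coherent, but the SAP would then have to define one-sided p-values and a direction of benefit for each endpoint, and amend the secondary alternative in SAP 3. The two-sided version needs less change.

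The cost is a few lines of SAP text. No data collection, sample size or primary analysis changes, and the familywise level stays within the stated 5%. Compared with the literal one-sided reading, power is unchanged; compared with the halving reading, the lost power is recovered.

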3.2. Interim Analysis

No interim analysis planned.

Population	Definition / Criteria	Analyses
		Evaluated
Safety analysis set	 All randomized subjects who received at least one dose of HB-adMSCs infusion or placebo. If participants receive a treatment different to their randomized treatment, they will be analysed according to the treatment actually received. 	 Safety Study Population
Efficacy analysis set	 All randomized participants who received all 4 infusions of HB-adMSCs or placebo. Participants will be analysed according to their randomized treatment. 	• Efficacy
Screened Population	 This population consists of all subjects who signed an ICF to participate in the clinical trial. This population will be used for summarizing screening failures and reasons for screening failures. 	Study Population

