- Incidence of treatment-emergent Adverse Events (TEAEs) and serious Adverse Events (SAEs).
- Incidence of AEs of special interest (serious or nonserious), including thromboembolic events, infections, and hypersensitivities.
- Changes in laboratory values, vital signs, weight, physical exam results, and medications used to treat Chronic Post-COVID-19 Syndrome.

Secondary Endpoints

The efficacy and safety secondary endpoints of this study will be evaluated by assessing changes from Baseline to Weeks 26 in the following:

- Subject's energy and stamina as evidenced on the Fatigue Assessment form.
- Visual Analog Scale of non -Neurological Symptoms. The symptoms included in this scale are (1) dyspnea at rest and with activity, (2) cough, (3) body aches, and (4) joint pain.
- Subject's quality of life as evidenced by the Short Form 36 Health Survey Questionnaire.
- Subject's level of depression as evidenced by the PHQ 9 scale.

Investigational Plan.

[figure not shown]
This study is a randomized, double-blind, single-center, phase 2 clinical trial to assess the efficacy and safety of multiple HB-adMSCs (allogeneic) vs. Placebo for treating Chronic PostCOVID-19 Syndrome. The trial includes a screening period of up to 4 weeks, a 10-week treatment period, and a safety Follow-up period of 16 weeks after the last investigational product administration.

This clinical trial will be opened to enroll 80 eligible participants diagnosed with Chronic PostCOVID-19 Syndrome. The study team will conduct patient recruitment. If eligible participants are identified based on eligibility criteria, a screening visit will be scheduled. An informed consent form will be given to the study participants and signed before any study procedures. The informed consent form will include information about the clinical trial, and some aspects should be considered during this process.

- The principal investigator or study team will make sure the participant was alert and able to read and understand the language in the consent form.
- The principal investigator or study team will ensure the participant took ample time to read the consent form carefully.
- The principal investigator or study team will make sure the consent form was carefully explained to the participant, and any questions or concerns were addressed before signing the document.

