- Visit 8 – End of Study, during this final visit (approximately 26 weeks after Week 0), an entire group of study assessments will be performed to evaluate the safety and efficacy of HB-adMSCs (allogeneic) or Placebo administrations.

Clinical assessments of disease activity will take place during the following visits:

- Visit 1 – Screening
- Visit 2 – Infusion 1 → **(Baseline)**
- Visit 3 – Infusion 2
- Visit 4 – Infusion 3
- Visit 5 – Infusion 4
- Visit 6 – Follow Up 1
- Visit 7 – Follow Up 2
- Visit 8 – End of Study

Blood samples for safety evaluations will be obtained at the following visits:

- Visit 1 – Screening. After informed consent has been obtained, laboratory samples will be drawn by venipuncture; the findings of the lab tests will be used to determine whether the individual is eligible for the research.
- Visit 2 – Infusion 1 **(Baseline)**: safety laboratory samples will be drawn by venipuncture to establish a baseline for comparison with the laboratory results obtained in subsequent visits.
- Visit 5 – Infusion 4: safety laboratory samples should be collected by venipuncture during this visit.
- Visit 8 – End of Study: safety laboratory samples should be collected by venipuncture during this visit.

Suppose a study participant receives at least one dose of the experimental drug and decides to withdraw consent after that. In that case, investigators should conduct a safety follow-up visit with this subject's approval to comply with the Sponsor's standard operating procedures.
--

Withdrawal Criteria

In different situations, a study subject may withdraw from the study before the planned completion of the visits. One of these situations is mentioned below,

1. Voluntary withdrawal: the subject doesn't want to continue receiving the investigational product.

The principal investigator and designated staff must record the reason for the subject's withdrawal on the case report forms, specifically in the Early Termination Visit or a Note to File Form.

Study participants discontinued from the clinical trial who received at least one infusion (HBadMSCs - allogeneic or placebo) will be invited to a Safety Follow-up visit.

Any withdrawal must be documented in the source documents and electronic case report forms. If the reason for the discontinuation is an adverse event or serious adverse event, the event must be followed until resolution by the principal investigator.

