All adverse events that do not meet any of the criteria for serious should be regarded as *nonserious adverse events*.

Adverse Event Reporting Period

The study period during which adverse events must be reported is typically defined as the period from the initiation of any study procedures to the end of the study treatment follow-up. For this study, treatment follow-up is described as approximately 16 weeks following the last administration of study treatment.

Stopping Rules

Infusion Stopping Rules

Study treatment infusion will be stopped if a least one of the following events occurs:

1. Allergic reaction as evidenced by severe dyspnea (defined as intense tightening of the chest, air hunger, breathlessness or feeling of suffocation), bronchospasm (defined as coughing, wheezing, difficulty breathing) or hypoxia (defined as pulse oximeter reading of less than 90%) after the product has been administered intravenously.
2. Hypersensitivity reactions such as rash, urticaria, itching, angioedema, nausea, vomiting, hypotension, or any evidence of anaphylaxis.
3. The patient verbally declines the treatment at any moment prior, or during the infusion.
4. Any febrile reaction will be an indicator for pausing the infusion for further evaluation.
5. Malignant Systolic blood pressure (SBP) greater than 170 and/or diastolic blood pressure greater than 100. SBP less than 80mm/Hg and/or DBP less than 40mm/Hg. *
6. Sudden Severe Hypotension (40 mm/Hg drop from infusion starting baseline) or systolic blood pressure <80mmHg.
7. Respiratory distress defined as having an acute sudden onset of shortness of breath or increased work of breathing, SaO₂ less than 90% or a respiratory rate >22 or < 10 breaths per minute. Any increased oxygen support that could indicate imminent respiratory failure.
8. Sudden increase or decrease in pulse rate of 30 bpm or more from infusion starting baseline or an absolute tachycardia of greater than 140 bpm or absolute bradycardia less than 45 bpm.
9. Change in neurologic status from infusion starting baseline including alertness.
10. The Principal Investigator may stop the infusion at any time, based upon PI's discretion.

*Any blood pressure from baseline exceeding or falling below $\pm 20\%$ of baseline or $\geq 140/90$ will necessitate a pause for evaluation.

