Suppose an infusion is stopped for a subject due to an adverse event or serious adverse event, including but not limited to hypersensitivity reaction/anaphylaxis. In that case, no additional study treatment will be given to the study participant who develops the event. Although the study participant will not

receive the investigational product, he or she must be followed for safety purposes according to the protocol.

Study Stopping Rules

This Clinical Trial will stop if any of the following events are present:

1. Subject's Death.
2. Any thromboembolic event will cause a pause in the study until an evaluation can be done by the DSMB, Principal Investigator and Medical Monitor to determine relationship.
3. Any cerebrovascular ischemia or seizure event occurring within 72 hours after any of the investigational product administrations.
4. Any Serious Adverse Events of the following:
 - When there is one CTCAE.v5 grade 4 or 5 AE, irrespective of attribution.
 - Either any CTCAE Grade 2 adverse event that persists for more than two weeks or any Grade 3 adverse event that occurs within 72 hours after product administration.

Should the study participant discontinue study treatment, he/she will be followed for safety according to the protocol safety monitoring plan. The study participant will receive follow-up communication via phone calls or electronically to ascertain the outcome until resolved fully. All will be documented as per protocol.

FDA shall review all changes to the study-stopping rules. If the study is suspended for any reason, it will not be re-opened until FDA agrees. Whether the study is stopped or suspended, all subjects will be followed to the EOS visit.

Statistical Methods

The sample size consists of 80 subjects who have been diagnosed with Chronic Post-COVID-19 Syndrome. All data collected from subjects who are enrolled and received the investigational product will be analyzed. The incidence of Adverse Events and Serious Adverse Events will be recorded and reported. Efficacy will be measured by improving the subject's signs and symptoms associated with Chronic Post-COVID-19 Syndrome. Interim analysis of all safety and efficacy data may be performed at any time deemed appropriate by the Sponsor. Data may be analyzed for internal informational purposes, reports, presentations, and manuscripts.

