5.1.2. Baseline Definitions

For all endpoints, the baseline value will be the latest pre-treatment assessment visit with a non-missing value. i.e., If an assessment has been made both at screening visit (Visit 1) and Week 0 infusion 1 visit (Visit 2, Week 0), the value from the Week 0 visit is used as the baseline value. If the value measured at the Week 0 visit is missing and the assessment also has been made at screening, then the screening value is used as the baseline value.

Unless otherwise stated, if baseline data is missing no derivation will be performed and baseline will be set to missing.

5.2. **Primary Endpoint(s) Analyses**

The primary objective of this study is to compare HB-adMSCs to Placebo on change in Visual Analog Scale of Neurological Symptoms scores. Efficacy analysis set will be used for this analysis. The details of the planned displays are in programming specification document.

5.2.1. **Definition of endpoint(s)**

Objectives	Endpoints
Primary Objective	Primary Endpoint
To investigate the efficacy of intravenous infusions of HB-adMSCs (allogeneic) vs. Placebo in patients with Chronic Post-COVID-19 Syndrome as determined by improvements in individual symptom scores of Visual Analog Scale of Neurological Symptoms. (Time frame: Baseline to Week 26).	Changes in the Visual Analog Scale of Neurological Symptoms. VAS are psychometric measuring tools intended to document the characteristics of disease-related symptom severity in individuals. The neurological symptoms included in this scale are (1) extreme fatigue (2) brain fog, (3) headache (4) sleep disturbances (5) loss of taste/smell.

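### The only efficacy set is four-infusion completers, so the primary superiority test excludes participants on post-randomisation events and no wider efficacy analysis stands behind it

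*SAP*

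**What the plan says.** The table of analysis sets (SAP Section 4) has three rows. The Safety set holds everyone randomised who had at least one dose, and serves safety and study population summaries. The Screened set serves screen failures. The Efficacy set is "All randomized participants who received all 4 infusions of HB-adMSCs or placebo", analysed by randomised arm, and is the only set assigned to efficacy.

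SAP 5.2 says of the primary comparison: "Efficacy analysis set will be used for this analysis". No other set is named for the repeated-measures model or paired tests (SAP 5.2.2) or for the secondary endpoints (SAP 5.3). The primary ANCOVA uses the Week 26 values that are available, and no missing-outcome method or sensitivity analysis is given.

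On the protocol side:

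- **Stopped infusions** (Infusion Stopping Rules). After an infusion is stopped for an adverse event, "no additional study treatment will be given to the study participant who develops the event", although "he or she must be followed for safety purposes according to the protocol". The triggers include "Hypersensitivity reactions such as rash, urticaria, itching, angioedema, nausea, vomiting, hypotension, or any evidence of anaphylaxis".
- **Primary Endpoints.** These include "Incidence of AEs of special interest (serious or nonserious), including thromboembolic events, infections, and hypersensitivities".
- **Withdrawal Criteria.** A participant who does not "want to continue receiving the investigational product" may leave.
- **Statistical Methods.** "All data collected from subjects who are enrolled and received the investigational product will be analyzed".

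SAP 5.4 declares no departure from the protocol's analysis. SAP 7.1.2 mentions a randomised analysis set for the demographic summaries, but the table does not define it.

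**The concern.** Infusions are given at Weeks 0, 2, 6 and 10, so nobody is known to belong to the efficacy set until Week 10. A stop for an adverse event at infusion 1, 2 or 3 removes the participant, and so does a voluntary withdrawal before infusion 4. The comparison is allogeneic cells against saline, and some stopping events are ones the protocol itself singles out as of special interest. Unequal exclusion is therefore plausible, though not established.

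The superiority test then compares completers, and randomisation no longer protects that comparison. Analysing by randomised arm settles which arm a retained participant counts in; it does not bring back those removed. Tabulating withdrawal reasons by arm (SAP 7.1.1) would reveal an imbalance but would not correct the estimate. If a reaction to an infusion itself worsened symptoms, the affected participants would be absent from every efficacy analysis, even those who attended Week 26 and completed the VAS.

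**Working it through.** **Inputs from the documents.** 80 participants (SAP 6), 1:1 allocation (SAP 2.2), so 40 per arm; two-sided 0.05 (SAP 5.1.1); VAS from 0 to 10 cm (Protocol, Visual Analog Scale of Symptoms). Neither document gives an effect size, SD, power or dropout rate, so the plan has no figure to reproduce here, and everything below is illustration.

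**Assumptions.** No true effect; SD 2.5 cm; baseline to Week 26 correlation 0.5. A poor-prognosis subgroup, whose Week 26 score is d cm worse, makes up the same share pA of both arms. All of it is excluded from the active arm, and a fraction pP/pA of it from placebo, so the exclusion rates are pA and pP.

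**Closed form.** Active completers contain none of the subgroup. Placebo completers still contain a share (pA - pP)/(1 - pP). Hence

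bias = -d × (pA - pP)/(1 - pP),

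where negative favours HB-adMSCs. The simulation used ANCOVA on baseline with 10,000 trials per row:

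| Excluded, active vs placebo | d (cm) | Closed form (cm) | Simulated bias (cm) | Type I error |
|---|---|---|---|---|
| 10% vs 5% (4 vs 2) | 2 | -2 × 0.05/0.95 = -0.105 | -0.096 | 5.1% |
| 15% vs 5% (6 vs 2) | 2 | -2 × 0.10/0.95 = -0.211 | -0.208 | 6.4% |
| 15% vs 5% (6 vs 2) | 4 | -4 × 0.10/0.95 = -0.421 | -0.417 | 10.9% |
| 10% vs 10% | 3 | 0 | -0.003 | 4.9% |
| 15% vs 5%, unrelated to outcome | 0 | 0 | -0.006 | 5.0% |

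Repeat runs agree within simulation error: about 5.6% for the first row, 6.2% to 6.8% for the second and 11% to 12% for the third. With everyone dosed included and Week 26 fully observed, bias is within 0.01 cm and type I error is 4.6% to 5.1%.

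**When the reaction causes the worsening.** With 15% against 5% reacting and a 4 cm worsening, the true all-dosed difference is 4 × (0.15 - 0.05) = +0.40 cm. Simulated, the all-dosed analysis gives +0.392 and the completer analysis -0.010, so the harm disappears.

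**Cross-check under a different assumption.** Exclude a share q from the active arm only, with retained participants g SD better on average than those excluded. The shift is q × g, the retained variance is 1 - q(1 - q)g², and SE = √[(1 - q(1 - q)g²)/(40(1 - q)) + 1/40].

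- q = 10%, g = 1: shift 0.10 SD; SE = √(0.91/36 + 1/40) = 0.224; type I error 7.3%.
- q = 20%, g = 1: shift 0.20 SD; SE = √(0.84/32 + 1/40) = 0.226; type I error 14.3%.
- q = 5%, g = 0.5: shift 0.025 SD; type I error 5.1%.

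**How far the remedy goes when scores are missing.** This uses a repeated-measures model at Weeks 2, 6, 10 and 26 on all dosed participants, with unstructured covariance, 2,000 trials and a simulation error of about 0.01 cm. The deficit was 50%, 75%, 100% and 100% of d at the four visits. Participants with missing data lack Weeks 10 and 26 but keep Weeks 2 and 6.

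| Scenario | Share of excluded who lack later scores | All-dosed bias (cm) | Completer bias (cm) |
|---|---|---|---|
| 10% vs 5%, 2 cm | half | -0.030 | -0.108 |
| 15% vs 5%, 2 cm | half | -0.078 | -0.219 |
| 15% vs 5%, 4 cm | half | -0.095 | -0.412 |
| 15% vs 5%, 4 cm | all | -0.261 | -0.426 |

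If those in the last row keep only Week 2, the all-dosed bias is about -0.33 cm. If they have no post-baseline VAS it is about -0.42 cm, which is no gain.

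**Precision.** The detectable difference at 80% power is (1.960 + 0.842) × √(2/40) = 0.63 SD with all 80. If 10% or 20% were excluded, leaving 72 or 64, it would be 0.66 or 0.70 SD.

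**The case against.** The strongest reply is about size. The scenarios that favour HB-adMSCs remove the whole poor-prognosis subgroup from one arm and only a third to a half of it from the other. The 10.9% also needs a 4 cm deficit, or 4/2.5 = 1.6 assumed SDs. At 2 cm the bias is 0.10 to 0.21 cm, against the SAP's own 1.9 threshold for clinical importance. Participants and site staff are blinded, both arms share the same pre-medication and stopping rules, and many triggers (blood pressure, pulse, a participant declining) can occur with saline. If exclusions fell mainly in placebo, the bias would reverse. All of this stands: size and direction are unknown. It does not supply the missing wider analysis.

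The protocol sentence on analysing all data is general and names no efficacy population, so it is a reason to reconcile the documents rather than proof on its own. Even so, an efficacy set narrower than that sentence should not sit beside a declaration of no departure.

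On the remedy, the SAP's repeated-measures model lists Weeks 14 and 20, which are phone calls with no VAS in Protocol Table 1, and pairs an unstructured covariance with a random subject effect. Both need tidying before the model is used, but they are separate defects; the contrast can be estimated from Weeks 2, 6, 10 and 26. ANCOVA on the wider set would also repair the set definition, though it uses only observed Week 26 values.

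Finally, follow-up according to the protocol may already include the End of Study VAS. The qualification that follow-up is for safety leaves this ambiguous, which is why it should be stated.

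**Conclusion.** The concern holds and should be corrected before the analysis. The primary superiority test is confined to a set defined by post-randomisation events, at least one route out of that set may depend on treatment, and nothing wider is planned to check the result.

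That conclusion rests on the text alone. The size does not: in the subgroup illustrations it runs from no bias, when exclusion is equal or unrelated to outcome, to -0.42 cm with roughly 11% type I error under a 15% against 5% imbalance and a 4 cm deficit. A more moderate 2 cm deficit gives -0.10 to -0.21 cm and about 5% to 7%. The case that matters most is the one in which a reaction worsens symptoms, because the planned analysis could not show it.

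**What to change.** - **Set.** Define the primary efficacy set as all randomised participants who received at least one infusion, by randomised arm and whatever the number of infusions. This agrees with the protocol's statistical section; all randomised would also do. Name the one chosen.
- **Data.** State that the scheduled Week 26 VAS is sought from participants whose infusions have stopped. The gain depends on this.
- **Estimate.** Take the Week 26 contrast from the SAP's repeated-measures model on this set, using the visits at which VAS is collected.
- **Sensitivity.** Add one analysis for missing Week 26 scores, for example delta-adjusted multiple imputation.
- **Supportive analysis.** Keep the four-infusion set as per-protocol, and say whether a partly delivered infusion counts.
- **Consistency.** Declare the change in SAP 5.4, and define or delete the randomised analysis set in SAP 7.1.2.

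The cost is wording in SAP Sections 4, 5.2, 5.4 and 7.1.2, one added analysis, and a statement on collecting the VAS after infusions stop. No dose or stopping rule changes. Partly treated participants will dilute the effect somewhat, and some Week 26 scores will still be missing after withdrawal, so bias is reduced rather than removed.
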